Research Proposal
[name], DO
WSU-SOM, OBGYN, PGY-2

Title

- Postpartum management of gestational hypertensive disorders using furosemide: A randomized controlled trial

Investigators

- Primary Investigator
 - [name], DO, PGY-2, Capt, USAF
 - [contact]
 - [contact]
- Investigators
 - [name], MFM subspecialist at MFMUG
 - [contact]
 - [contact]
 - [name], WSU-SOM Teaching Faculty
 - [contact]
 - [contact]

Summary

- The main purpose of this study is to learn if incorporating a loop diuretic such as furosemide along with labetalol in the routine management of postpartum gestational hypertensive disorders could lower the need for additional anti-hypertensive agents to control blood pressures, improve blood pressures (as measured by systolic blood pressure, diastolic blood pressure and mean arterial blood pressures), shorten hospital stays and decrease readmissions for patients with gestational hypertensive disorders.
- Based on a study by Veena et al¹, there is reason to believe that the addition of furosemide to other anti-hypertensives may help decrease the need to add or increase the dose of medication to control blood pressures. There may be potential to shorten hospital stays and decrease readmissions, as well. Collecting data will be done using a prospective, randomized 1:1 controlled study assigning postpartum patients with a gestational hypertensive diagnosis to either labetalol alone or labetalol plus furosemide.
- Based on an estimated 8% need for increase in anti-hypertensive medication in the furosemide group and a 26% need in the standard treatment arm, to achieve 90% power

with a 2-sided alpha of 0.05, we calculate 96 patients per group. Analysis will be via Chi-square or Fisher's exact test for categorical variables. Student T-Test and Mann Whitney U tests will be utilized to compare continuous variables. Randomization will be performed using REDCap.

- The study will be performed in the postpartum wing of Miami Valley Hospital Main Campus and would recruit patients who have consented to participate in the study with enrollees coming from the OB Staff population.

Background and Literature Review

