- We found four studies investigating loop diuretics in the management of postpartum hypertensive disorders- Matthews et al², Ascarelli et al³, Amorim et al⁴, and Veena et al. Of these studies, only Amorim and Veena were able to show statistical significance on any parameters. Amorim was able to show that there was an improvement of SBP, DBP and MAP, but their research was only presented as an abstract at a conference and not published, thereby making it impossible to draw any conclusions or practice guidelines. Veena demonstrated that by using furosemide and nifedipine in combination, the need for additional antihypertensive medication in severe pre-eclampsia in the postpartum period was reduced when compared to nifedipine alone.
- A systematic review⁵ of postpartum hypertensive disorder management suggested that there was insufficient data to recommend any single pharmacological intervention at this time in the management of gestational hypertensive disorders. The review emphasized the need for further studies to be conducted to help guide management of patients affected by gestational hypertensive disorders in the future.

Objectives

- **Main Question**
 - Does the use of furosemide plus labetalol improve blood pressures in the postpartum period of patients with gestational hypertensive disorders versus labetalol alone?
 - **Primary**
 - Does the addition of a 5-day course of furosemide to labetalol avoid the escalation of anti-hypertensive therapy to control blood pressures.
 - **Secondary:**
 - Does the addition of furosemide to labetalol in postpartum hypertension:
 - Improve of systolic blood pressure, diastolic blood pressure and mean arterial pressure.
 - Shortened hospital stay
 - Affect breastfeeding status at 1 week postpartum visit in mothers planning to breastfeed.
 - Decrease readmission for postpartum hypertensive disorders.

Significance to patient, institution, and profession

- As a busy referral center with a level 3 NICU, Miami Valley care for a large number of patients with gestational hypertensive disorders
- The majority of the OB staff population being served at Miami Valley Hospital is African American. According to Myatt⁶, the incidence of pre-eclampsia in the African American population is greater than double the Caucasian population (11% to 5%) thereby making this study very applicable to our patient population.

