- With the construct of the study, we would be keeping costs low by utilizing already established resources and practices (blood pressure cuffs, nurses, routine one week blood pressure checks) while only adding on the unit cost of furosemide and basic metabolic panels.
- If treatment with labetalol and furosemide is found to be useful, it would be not only a very inexpensive, cost effective way of improving patient outcomes and possibly decreasing lengths of stay, but possibly improvement in global practice in places that are lacking in resources privy to first world countries.

Methods

- A prospective randomized 1:1 controlled trial including postpartum women with gestational hypertension or preeclampsia
 - Inclusion criteria: Age 18-45, Postpartum: 24-72 hours after delivery, no contraindications to the study medications
 - Exclusion criteria: chronic hypertension diagnosis, creatinine levels above 1.5 $\mu\text{m}/\text{L}$, unable to give consent
- One arm receiving 200mg labetalol BID alone on Day#1 or at least 24 hours after magnesium sulfate, if given
- One arm receiving 200mg labetalol BID and a five day course of furosemide 20mg QD on Day#1 or 24 hours after magnesium sulfate
 - The 20 mg dose is the standard dose for furosemide in this population.
- Titrate labetalol to maintain blood pressures below 150 SBP and/or 100 DBP per ACOG recommendations.⁷
 - In the event of persistently elevated blood pressures, labetalol will be increased to 400mg BID and escalated to 600mg BID and finally 800mg BID as indicated
- Measurement of blood pressure every four hours until patient discharge
- Daily BMPs to assess for electrolyte abnormalities
- Measurement of urine output every 12 hours until discharge
- Demographics
 - Age (18-24, 25-34, 35-44, 45-51)
 - Nulliparous (yes, no)
 - BMI (underweight, normal, overweight, obese)

- Race (Caucasian, African American, Asian, Hispanic, Other)
- Diabetes (yes, no)
- Multiple gestation (yes, no)
- Preterm delivery (yes, no)
 - Gestational age at delivery
- Cesarean delivery (yes, no)
- IVF pregnancy (yes, no)
- History of previous gestational hypertension/pre-eclampsia (yes, no)
- Systemic lupus erythematosus (yes, no)
- Renal disease (yes, no)
- Outcome variables
 - Need for additional antihypertensive medication (yes, no)
 - Labetalol 400mg BID
 - Labetalol 600mg BID
 - Labetalol 800mg BID
 - Highest systolic blood pressure (mmHg)
 - Highest diastolic blood pressure (mmHg)
 - Mean arterial blood pressure

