 - Daily urine output (mL)
 - Length of postpartum stay (days)
 - Readmission for hypertension (yes, no)
 - Breastfeeding at 1 week postpartum (yes, no)
- The study duration is the length of the hospital stay plus 1 week postpartum blood pressure check.
- The research will be analyzed and interpreted by the research team conducting the study.
- Potential difficulties and limitations include compliance concerns of mandatory one week blood pressure follow up appointment.
- The unit cost of one tablet of labetalol 200mg and furosemide 40mg is currently \$0.32 and \$1.23, respectively.^{8,9}
- The study would use already readily available automated blood pressure cuff machines on the postpartum wing.

Safety Monitoring

Monitoring of blood pressures will be performed every four hours while on the maternity postpartum floor. If the patient is found to be above 160 systolic or 110 diastolic, it will be rechecked in fifteen minutes. If still elevated, then escalation of blood pressure medicine will be done. The healthcare provider will ask the patient if they are exhibiting any signs of profound hypertension and/or hypokalemia including headache, vision changes, dizziness, lightheadedness, weakness, fatigue, muscle cramping, or heart palpitations. If any of these are identified, a physician will be notified and will assess the patient.

Patients will be instructed to let their doctor/nurses know if they are experiencing known side effects of Lasix that include new onset weakness, fatigue, muscle cramping, dizziness or

heart palpitations. If a patient has severe symptoms after discharge, they will be instructed to call the afterhours phone number on the consent form.

If a patient has signs of hypokalemia, we will test lab values for potassium (K+) levels (Complete metabolic panel). We will continue administering Lasix if the potassium result is between 3.0 and 3.4 $\mu\text{m}/\text{L}$ and we will administer 20 mEq KDur BID. If it is less than 3.0 $\mu\text{m}/\text{L}$ we will stop using Lasix.

References

- 1) Veena, P., et al. “Furosemide in Postpartum Management of Severe Preeclampsia: A Randomized Controlled Trial.” *Hypertension in Pregnancy*, vol. 36, no. 1, 2016, pp. 84–89., doi:10.1080/10641955.2016.1239735.

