Postpartum management of gestational hypertensive disorders using furosemide: A randomized controlled trial

Statistical Analysis Plan

Version Jan 9, 2020

[name]; [name], DO; [name]

The statistical analysis plan is based on the objectives of the study as follows:

Main Question: Does the use of furosemide plus labetalol improve blood pressures in the postpartum period of patients with gestational hypertensive disorders versus labetalol alone?

Primary:

Does the addition of a 5-day course of furosemide to labetalol avoid the escalation of anti-hypertensive therapy to control blood pressures.

Analysis plan: Randomization groups (labetalol + furosemide vs labetalol alone) will be compared using a Fisher's Exact test for number of patients who have had an escalation of labetalol dose at any time during their hospital stay.

Secondary:

Does the addition of furosemide to labetalol in postpartum hypertension:

1. Improve of systolic blood pressure, diastolic blood pressure and mean arterial pressure.

Analysis plan: Randomization groups will be compared on daily means for each outcome by repeated measures ANOVA to determine difference in outcomes across time (Day 0/Baseline, Day 1, and Day 2). One repeated measures ANOVA will be performed for each of the three outcomes (systolic blood pressure, diastolic blood pressure, and mean arterial pressure).

2. Shortened hospital stay

Analysis plan: Randomization groups will be compared on hospital length of stay using a Student T-test.

3. Affect breastfeeding status at 1 week postpartum visit in mothers planning to breastfeed.

Analysis plan: Randomization groups will be compared on breastfeeding status at the postpartum visit using a Fisher's Exact test.

4. Decrease readmission for postpartum hypertensive disorders.

Analysis plan: Randomization groups will be compared on the number of participants who were hospitalized after discharge using a Fisher's Exact test.

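### Secondary objective 3 is limited to women who plan to breastfeed, but neither document lists that plan as a variable or says when it is recorded, and the SAP test is not restricted to them

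*Protocol*

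**What the plan says.** - **Objective.** Protocol, Objectives, Secondary: "Affect breastfeeding status at 1 week postpartum visit in mothers planning to breastfeed". The SAP repeats this as Secondary item 3.
- **Baseline list.** Protocol, Methods, Demographics runs item by item from age to "Renal disease (yes, no". It includes IVF pregnancy and lupus, but neither intended nor current feeding.
- **Outcome list.** Protocol, Methods, Outcome variables has one feeding item: "Breastfeeding at 1 week postpartum (yes, no".
- **Analysis.** SAP, Secondary item 3: "Randomization groups will be compared on breastfeeding status at the postpartum visit using a Fisher's Exact test". This sentence has no denominator rule and names no source for intention.
- **Entry window.** Protocol, Methods, inclusion criteria: "Postpartum: 24-72 hours after delivery".
- **Arms.** Protocol, Methods: "One arm receiving 200mg labetalol BID alone on Day#1" against "One arm receiving 200mg labetalol BID and a five day course of furosemide". Neither placebo nor blinding is mentioned.

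**The concern.** The population named in the objective is defined by a characteristic that appears in neither variable list. Adding a restriction to the SAP sentence would not be enough by itself, because the restriction needs a value fixed before treatment could influence it.

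If that value is missing at analysis, the team has two routes. It can analyse all women, so that those who never meant to breastfeed add non-events to both arms and the absolute difference shrinks. Or it can establish intention afterwards, when a woman already knows how feeding went and, with no blinding described, probably knows whether she took a diuretic. Selecting on such an answer gives up the protection of randomisation for this comparison.

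This is the only listed outcome on infant feeding. An uninformative or distorted result here would not be made good elsewhere in the plan.

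**Working it through.** **The plan's own figure.** No sample size or power is stated for breastfeeding. The stated 96 per group is for the primary outcome (8% v 26%, 90% power, two-sided alpha 0.05; Protocol, Summary). Exact power of the two-sided Fisher test, summing binomial probabilities over all tables with p ≤ 0.05, is 90.3% at 96 per group. The figure reproduces, and this point does not change it.

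**Assumptions (the documents give no rates).**
- Share planning to breastfeed, π: 60%, 70% or 80%.
- Breastfeeding at 1 week among planners: 80% on labetalol alone, 60% with furosemide.
- None among non-planners.
- No missed visits.

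**Route 1: all women analysed.** Planners per arm = 96 × π, rounded. The rate in all women = π × the rate in planners. Power is exact two-sided Fisher.

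| π | Planners per arm | Power, planners (80% v 60%) | Rates in all 96 per arm | Power, all women |
|---|---|---|---|---|
| 60% | 58 | 59% | 48% v 36% | 33% |
| 70% | 67 | 66% | 56% v 42% | 44% |
| 80% | 77 | 73% | 64% v 48% | 55% |

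The true 20-point difference appears as 12, 14 or 16 points.

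The loss does not depend on the 20-point effect. At 80% v 65% among planners, the same calculation gives 37%, 42% and 49% in planners against 20%, 26% and 33% in all women.

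**Route 2: intention obtained after treatment starts.** Take 100 true planners per arm. On labetalol alone 80 are breastfeeding and 20 have stopped; with furosemide the figures are 60 and 40. Suppose some who stopped are recorded as never having planned to, and so leave the denominator. The observed rate is then breastfeeding / (100 − number removed).

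| Removed | Labetalol alone | With furosemide | Observed gap (true 20) |
|---|---|---|---|
| 10 in furosemide arm only | 80/100 = 80.0% | 60/90 = 66.7% | 13.3 |
| A quarter of those who stopped, both arms (5 and 10) | 80/95 = 84.2% | 60/90 = 66.7% | 17.5 |
| 10 in each arm | 80/90 = 88.9% | 60/90 = 66.7% | 22.2 |
| 10 in control arm only | 80/90 = 88.9% | 60/100 = 60.0% | 28.9 |

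The observed gap can fall below or above the true one. With no true difference (80% in both arms), removing 10 women from the furosemide arm alone gives 80/90 = 88.9% v 80%, a spurious 8.9 points.

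**The case against.** **The lists may not be the whole dataset.** This stands. The SAP analyses daily mean pressures including Day 0/Baseline, yet no baseline pressure appears in the Protocol's lists. Daily metabolic panels are collected but are also unlisted. No case report form is among the documents, and intention may be in routine hospital notes. A reader might infer that the data do not exist or that the denominator cannot be formed. The documents support only that the source and timing of intention are unspecified.

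**The direction of error is unknown.** This also stands. A reader might infer that both routes favour furosemide. That needs misreporting concentrated in the furosemide arm, for which the documents give no support; other patterns exaggerate a harm. The objective's wording is neutral, and the documents do not say that furosemide is expected to reduce breastfeeding.

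**Analysing everyone is not invalid.** Agreed. It keeps the randomised comparison and the type I error. It answers a broader question than the stated objective, with less sensitivity. That is dilution, not bias.

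**The rates are invented, and the fix leaves power below 80%.** Both are true of every scenario shown. Missed 1-week visits, which the Protocol raises as a compliance concern, would lower power further. The fix makes the stated objective answerable; it does not make this outcome well powered.

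**Asking at the 1-week visit, and an open-label design, are inferences.** No text says intention will be asked then, and lack of blinding is read from silence. But no earlier recording is specified either, so nothing in the plan rules the second route out.

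**Conclusion.** The concern holds as a gap in specification. The objective is restricted to a subgroup whose defining variable has no stated source or time of recording, and the planned test does not apply the restriction. It is more than a wording gap, because once a woman has been allocated and treated, an answer unaffected by treatment can no longer be obtained by asking her.

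Under the stated assumptions (60-80% planning, 80% v 60% among planners, none among non-planners, no missed visits), analysing everyone lowers power from 59-73% to 33-55%. Restricting on a later answer can move a true 20-point gap to anywhere from 13.3 to 28.9 points in the examples shown. These figures illustrate size and are not estimates for this trial.

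One of four secondary objectives is affected. It should be corrected, but it does not threaten the primary result.

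**What to change.** 1. Add to the Demographics list in Protocol, Methods: *Plan to breastfeed (yes, no), recorded before randomisation*. Women enter 24-72 hours after delivery, so this can be asked at consent.
2. Add to SAP, Secondary item 3: *The Fisher's exact test is restricted to women who answered yes to this question before randomisation.*
3. For women already enrolled, use only intention charted before randomisation. Do not ask them in retrospect.

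A graded feeding-status field is not needed for the objective as stated.

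**Cost.** One extra baseline question, one SAP clause and a chart check for women already enrolled. The denominator falls, to about 58-77 per arm if 60-80% plan to breastfeed, before missed visits. The primary analysis and the 96 per group do not change.

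### SAP Secondary 4 counts any hospitalisation after discharge, although the stated outcome is readmission for hypertension, and neither document sets a readmission window

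*Protocol*

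**What the plan says.** **Outcome.** The protocol's secondary objectives include fewer readmissions for postpartum hypertensive disorders, and the outcome variables in Methods list "Readmission for hypertension (yes, no". The SAP repeats the objective as the heading of Secondary 4: "Decrease readmission for postpartum hypertensive disorders". The analysis sentence below that heading reads: "Randomization groups will be compared on the number of participants who were hospitalized after discharge using a Fisher's Exact test". It names no cause and no end date.

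**Follow-up.** No readmission window appears in either document. Methods says only: "The study duration is the length of the hospital stay plus 1 week postpartum blood pressure check". No later contact or chart review is described. Among limitations, the protocol mentions "compliance concerns of mandatory one week blood pressure follow up appointment".

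**Related outcome.** A shorter stay is a separate secondary objective: "Randomization groups will be compared on hospital length of stay using a Student T-test".

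**Entry and treatment.** Patients enter at "Postpartum: 24-72 hours after delivery". The furosemide course lasts five days, starting on Day 1 or 24 hours after magnesium sulfate.

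**The concern.** The rule that will be programmed is the analysis sentence. As written, it makes an admission for a wound infection an event in a comparison meant to show an effect on hypertension. Admissions unrelated to blood pressure would pull the risk ratio towards 1, and where few events are expected a handful of them could decide the result.

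The missing window is the second problem. An analyst would have to choose the cut-off after the data are in, or fall back on the study-duration sentence. The fallback has two consequences if the week is counted from delivery. Follow-up stops at about the time furosemide stops, so a readmission deferred until after the course would look like one prevented. Also, a patient can be readmitted only once she has gone home, so the arm discharged earlier is exposed for longer, and a comparison of simple proportions makes no allowance for that.

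**Working it through.** **1. The plan's own figure.** No rate or sample size is given for readmission. The stated 96 per group is for the primary endpoint (8% vs 26%, 90% power, two-sided alpha 0.05). Full enumeration of the two-sided Fisher test gives 89.9% power at 95 per group and 90.3% at 96, so that figure reproduces. It is not in question here.

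**2. Cause.**

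| Place | What is counted |
|---|---|
| Protocol, Objectives | Readmission for hypertensive disorders |
| Protocol, Methods, outcome variables | Readmission for hypertension |
| SAP, Secondary 4, heading | Readmission for hypertensive disorders |
| SAP, Secondary 4, analysis sentence | Hospitalisation after discharge, any cause |

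Three of the four agree, and the one that defines the test differs. To illustrate the effect, assume hypertension readmission of 2% on furosemide and 4% on control (ratio 0.50), plus an equal rate c of other admissions in each arm. The ratio actually tested is (2 + c)/(4 + c):

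- c = 1%: 3/5 = 0.60
- c = 2%: 4/6 = 0.67
- c = 4%: 6/8 = 0.75

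**3. Event numbers.** The rates are assumed, since the documents give none. The expected number of control events is 96 × rate. Exact Fisher power is for a halving at 96 per group.

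| Control vs furosemide | Control events | Power |
|---|---|---|
| 4% vs 2% | 96 × 0.04 = 3.8 | 4.0% |
| 6% vs 3% | 96 × 0.06 = 5.8 | 8.5% |
| 8% vs 4% | 96 × 0.08 = 7.7 | 13.4% |

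**4. Time after the last furosemide dose.** Assume that the study-duration sentence sets the cut-off, that the check is on day 7 from delivery, and that the first dose is on postpartum day 1, 2 or 3 (from the entry window). Last dose = first day + 4.

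- First dose day 1: last dose day 5, 7 − 5 = 2 days left
- First dose day 2: last dose day 6, 7 − 6 = 1 day left
- First dose day 3: last dose day 7, 7 − 7 = 0 days left

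A later start after magnesium sulfate could run past the check.

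**5. Dependence on discharge date.** Days at risk = 7 − discharge day. Risk = 1 − exp(−h × days), with the same daily hazard h in both arms. Discharge days and h are assumed.

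| h | Control day 3, furosemide day 2 (4 vs 5 days) | Control day 4, furosemide day 3 (3 vs 4 days) |
|---|---|---|
| 0.5% | 2.47%/1.98% = 1.25 | 1.98%/1.49% = 1.33 |
| 1% | 4.88%/3.92% = 1.24 | 3.92%/2.96% = 1.33 |
| 2% | 9.52%/7.69% = 1.24 | 7.69%/5.82% = 1.32 |

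With the window ending on day 42 from delivery (days at risk = 42 − discharge day), the same one-day shifts give a ratio of about 1.02. With a window of fixed length from discharge, the ratio is 1.00 by construction.

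**The case against.** **The SAP heading settles the cause.** It can be argued that the analysis sentence is only loose wording, since it sits under a heading about hypertensive disorders and the only readmission variable collected is specific to hypertension. That is probably the intention. But the sentence is the operative rule, and read literally it gives a different count.

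**The one-week cut-off is an inference.** A reader might conclude that readmission is counted only up to the 1-week check. No passage says so. The protocol attaches one week to breastfeeding and not to readmission, and the SAP gives readmission no end date. What stands is that the window is undefined.

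**Missed visits.** A reader might also infer that readmissions are lost when the check is missed. The attendance concern is about the blood pressure appointment, and nothing says that readmission is ascertained there. The gap is that no method of ascertainment is stated.

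**Unequal exposure.** A reader might call the comparison biased against furosemide. That needs a cut-off counted from delivery and a real effect on length of stay, which is only hypothesised. If the check falls one week after discharge, time at risk is a fixed 7 days and the argument disappears, although the word postpartum favours delivery. The numbers are also small: at 4% vs 5%, 96 per group differ by about one event (96 × 0.01) and Fisher's test rejects 2.4% of the time. The distortion could not create a false benefit. Moreover, the proportion readmitted by a fixed day after delivery, among all randomised patients, is a legitimate randomised comparison. This objection largely stands.

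**Off-drug follow-up.** No objective asks whether readmissions are prevented or merely delayed, so a longer window is a recommendation about interpretability. Low power for a secondary endpoint is not in itself a planning error.

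**Conclusion.** The point holds in a limited form. The mismatch of cause between the Secondary 4 analysis sentence and the stated outcome is plain from the text and needs no assumption. The absence of a readmission window is equally plain.

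The rest is conditional. If the study duration sets the cut-off and is counted from delivery, about 0-2 days remain after the last furosemide dose, and time at risk varies with discharge date. The apparent risk ratio of 1.24-1.33 also assumes discharge one day earlier from day 3 or 4 and equal constant hazards of 0.5%-2% per day. It illustrates direction and order of size and does not estimate bias in this trial. The documents do not support a claim that the readmission result will be biased, or that events in non-attenders will be lost.

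This is a minor but worthwhile correction to one secondary endpoint. The primary analysis and the 96 per group are untouched.

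**What to change.** In SAP Secondary 4:

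- Count readmission for hypertension, in agreement with the heading and the protocol variable.
- Take it from the hospital record for every randomised patient, whether or not the 1-week check was attended.
- State one fixed window from delivery or randomisation that ends well after the furosemide course. Six weeks is an example. It dilutes the dependence on discharge date (about 1.02 in the illustration) but does not remove it. A fixed length from discharge would equalise days at risk, but its clock starts at an event that treatment may move.
- Use all randomised patients as the denominator, keep Fisher's exact test, and add the risk difference with its 95% CI.

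The cost is a later chart review and a short amendment to the study duration in the protocol, with no extra visit. Readmissions to other hospitals may be missed, and the report should say so.

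### Furosemide's named symptoms are not collected on a common schedule in both arms or included in the SAP, so they cannot be compared fairly; a cheap improvement of minor severity

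*Protocol*

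**What the plan says.** **Symptoms.** Safety Monitoring opens with four-hourly blood pressure checks, then gives the recheck and escalation rule for readings above 160 systolic or 110 diastolic. Directly after that comes the staff question: "The healthcare provider will ask the patient if they are exhibiting any signs of profound hypertension and/or hypokalemia". It names dizziness, weakness, fatigue, muscle cramping and palpitations, among others, and a physician assesses any woman who reports one. No frequency, time point or recording step is given.

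**Self-report.** The next paragraph adds: "Patients will be instructed to let their doctor/nurses know if they are experiencing known side effects of Lasix". It lists these as "known side effects of Lasix that include new onset weakness, fatigue, muscle cramping, dizziness or" heart palpitations. That instruction has no severity limit. For the time after discharge the text says: "If a patient has severe symptoms after discharge, they will be instructed to call the afterhours phone number on the consent form".

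**Potassium.** Methods plans "Daily BMPs to assess for electrolyte abnormalities". Safety Monitoring has a replacement rule ("We will continue administering Lasix if the potassium result is between 3.0 and 3.4", with KDur added) and, below 3.0, a stop rule ("we will stop using Lasix").

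**Treatment and follow-up.** The furosemide arm receives "a five day course of furosemide 20mg QD on Day#1 or 24 hours after magnesium sulfate". The control arm receives labetalol alone, and no placebo or masking is described. Follow-up is the hospital stay plus a 1-week blood pressure check, to which no symptom question is attached.

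**Analysis.** The outcome variables in Methods are labetalol escalation, highest systolic and diastolic pressure, mean arterial pressure, urine output, length of stay, readmission for hypertension and breastfeeding. The SAP compares the arms on escalation, three blood pressure measures, stay, breastfeeding and hospitalisation after discharge.

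**The concern.** The trial asks whether furosemide should join labetalol in routine care after delivery. A reader of the results will want to see the drug's expected symptoms beside its benefit. For that comparison to be fair, women in both arms must be asked the same thing at the same times. The plan does not ensure this, for two reasons.

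- **In hospital the wording is ambiguous.** A nurse could ask at every four-hourly check, or only when a reading is raised. Under the second reading, the chance of being asked depends on blood pressure. If furosemide works, control women would then be asked more often.
- **After discharge there is no asking.** Capture depends on women who may know their treatment and who have been told which symptoms the drug causes.

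A symptom that was never asked about or volunteered cannot be recovered at analysis, and different amounts of asking in the two arms cannot be corrected afterwards.

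**Working it through.** **1. What is compared by arm.** SAP comparisons: 1 escalation + 3 blood pressure + 1 stay + 1 breastfeeding + 1 hospitalisation = 7. Comparisons of a named symptom: 0.

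**2. How much treatment may be taken at home.** Planned furosemide days are 96 x 5 = 480 (96 per group from the Summary, five days from Methods). Discharge on treatment day 1, 2, 3, 4 or 5 leaves 384, 288, 192, 96 or 0 days at home, or 80%, 60%, 40%, 20% or 0%. No document gives the discharge day, so only this range can be stated.

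**3. Whether the course ends before the 1-week visit.** Fifth dose = first dose + 96 h. Assumptions: the first dose falls in the 24 to 72 h eligibility window, or 24 h after magnesium that ended at 72 h; the visit is at 168 h.

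| First dose (h) | Fifth dose (h) | Visit minus fifth dose (h) |
|---|---|---|
| 24 | 120 | +48 |
| 72 | 168 | 0 |
| 96 (after magnesium) | 192 | -24 |

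Most courses would be finished or finishing at the visit, but a delayed start may not be.

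**4. Effect of incomplete capture.** All rates are assumptions. If a share c of symptoms is captured in both arms, recorded difference = c x true difference. For a true 15% v 5%:
- c = 0.3: 0.3 x 10 = 3 points
- c = 0.5: 7.5% v 2.5%, or 5 points
- c = 0.8: 0.8 x 10 = 8 points

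If the true rate is 10% in both arms but capture is 60% v 30%, the recorded rates are 6% v 3%, a false 3-point difference. With the capture rates swapped it is -3 points.

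**5. Asking only after a raised reading.** As a rough stand-in for the share of women with a persistently raised reading, take the Summary's escalation rates, 8% with furosemide and 26% with control. With a true symptom rate of 10% in both arms and no self-report, the recorded rates are 0.08 x 10% = 0.8% and 0.26 x 10% = 2.6%. The control arm would look worse by 1.8 points with no real difference. Self-report by women who know they take furosemide could push the other way, so the net direction is unknown.

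**6. Precision of a symptom table.** Newcombe 95% intervals for the risk difference:
- 96 per arm, 14 v 5 women: 14.6% - 5.2% = 9.4 points (0.8 to 18.3)
- 96 per arm, 10 v 5 women: 10.4% - 5.2% = 5.2 points (-2.7 to 13.5)
- 77 per arm (80% attendance assumed; 0.8 x 96 = 76.8), 11 v 4 women: 14.3% - 5.2% = 9.1 points (-0.5 to 19.1)

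Exact power of the two-sided Fisher test at 0.05 for 15% v 5% is 56% at 96 per arm and 46% at 77. For 10% v 5% at 96 it is 18%. The table should therefore be descriptive.

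**7. Potassium.** The lowest of several values falls as draws are added. For normal values the expected minimum is 0.564 SD below the mean with two draws and 0.846 SD below with three, a drop of 0.282 SD. At an assumed within-woman SD of 0.25 to 0.3 that is 0.07 to 0.08. A mean difference with 96 per arm and an assumed SD of 0.4 has a 95% half-width of t(190) x 0.4 x sqrt(2/96) = 0.11. One extra hospital day could thus imitate much of a detectable difference, so a fixed-day value is better.

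**8. The primary analysis.** The planned 96 per group reproduces: Fisher power for 26% v 8% is 89.9% at 95 per group and 90.3% at 96. Nothing in this point touches it.

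**The case against.** The case on the other side has four parts.

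- **The staff question may already have a schedule.** It sits in the paragraph on four-hourly checks, applies to both arms, and leads to a physician assessment that would normally be charted. This stands in part. The inpatient gap is an ambiguity, and it would be wrong to infer that symptoms go unasked in hospital. But the text does not exclude asking only after a raised reading.
- **Safety is not an objective.** The SAP follows the stated objectives, the protocol regards the dose as standard, and breastfeeding and hospitalisation after discharge may pick up some harm. This supports a minor rating. It does not supply the missing symptom data.
- **Potassium, KDur use and furosemide stops can be recovered.** This stands. In-hospital values are in the daily BMPs and the charts, so for these only a planned summary is missing.
- **The fix will not give a precise or unbiased answer.** This also stands. Intervals are wide, the protocol itself warns about compliance with the 1-week visit, and a checklist cannot stop women who know their treatment from reporting differently. It does make the asking equal.

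A reader might also infer that only severe symptoms are to be reported after discharge. The word severe governs only the after-hours number; the general instruction has no such limit. Nor do the documents support an inference that women are left unprotected: physician assessment, potassium thresholds and a stop rule are all present.

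**Conclusion.** The point holds for the named symptoms. In hospital the timing of the question is unclear. After discharge no asking is planned, although up to 80% of furosemide days could fall there. No symptom is an outcome variable or a SAP analysis. The trial as written therefore could not compare these symptoms fairly by arm.

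The size cannot be fixed from the documents. On the assumed rates, a true 10-point difference would be recorded as 3 to 8 points, or a false 3-point difference could appear in either direction. No direction of bias is claimed. The conclusion rests on the absence of a stated schedule, of symptom collection at the 1-week visit and of any described masking. It does not extend to the primary result, the sample size or the care of individual women. This is a cheap improvement of minor severity.

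**What to change.** **Protocol.** In both arms, ask the same five-symptom yes/no checklist (weakness, fatigue, muscle cramping, dizziness, palpitations) once daily at an existing blood pressure check, whatever the reading. Ask it again at the existing 1-week visit, covering the days since discharge, and note whether the five-day course is finished.

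**SAP.** Add one descriptive table by arm, without significance tests. For each symptom give the number asked, n, % and the risk difference with 95% CI. Show in-hospital and 1-week results separately, because fewer women will answer at one week.

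**Optional.** Tabulate potassium at a fixed treatment day, and counts of KDur use and furosemide stops. These are reporting additions from data already available.

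**Cost.** One protocol sentence, a few yes/no REDCap fields and one table. There are no new visits, blood draws or patients, and the seven planned comparisons do not change. The drawbacks are slightly more charting, wide intervals, non-specific postpartum symptoms reported in both arms, and remaining reporting bias if women know their treatment.
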